8.3.2. Post-study adverse events and serious adverse events

A post-study AE/SAE is defined as any event that occurs outside of the AE/SAE reporting period defined in [Table 21](#). Investigators are not obligated to actively seek AEs or SAEs in former study participants. However, if the investigator learns of any SAE at any time after a subject has been discharged from the study, and he/she considers the event reasonably related to the study vaccines/products, the investigator will promptly notify the Study Contact for Reporting SAEs.

8.3.3. Evaluation of adverse events and serious adverse events

8.3.3.1. Active questioning to detect adverse events and serious adverse events

As a consistent method of collecting AEs, the subject should be asked a non-leading question such as:

'Have you felt different in any way since receiving the vaccines/products or since the previous visit?'

When an AE/SAE occurs, it is the responsibility of the investigator to review all documentation (e.g. hospital progress notes, laboratory and diagnostics reports) relative to the event. The investigator will then record all relevant information regarding an AE/SAE in the eCRF. The investigator is not allowed to send photocopies of the subject's medical records to GSK Biologicals instead of appropriately completing the eCRF. However, there may be instances when copies of medical records for certain cases are requested by GSK Biologicals. In this instance, all subject identifiers will be blinded on the copies of the medical records prior to submission to GSK Biologicals.

The investigator will attempt to establish a diagnosis pertaining to the event based on signs, symptoms, and/or other clinical information. In such cases, the diagnosis should be documented as the AE/SAE and not the individual signs/symptoms.

8.3.3.2. Assessment of adverse events

8.3.3.2.1. Assessment of intensity

The intensity of the following solicited AEs will be assessed as described:

Table 22 Intensity scales for solicited symptoms

Adverse Event	Intensity grade	Parameter
Pain at injection site	0	None
	1	Mild: Any pain neither interfering with nor preventing normal every day activities.
	2	Moderate: Painful when limb is moved and interferes with every day activities.
	3	Severe: Significant pain at rest. Prevents normal every day activities.
Redness at injection site		Record greatest surface diameter in mm
Swelling at injection site		Record greatest surface diameter in mm
Fever*		Record temperature in °C/°F
Headache	0	Normal
	1	Mild: Headache that is easily tolerated
	2	Moderate: Headache that interferes with normal activity
	3	Severe: Headache that prevents normal activity
Fatigue	0	Normal
	1	Mild: Fatigue that is easily tolerated
	2	Moderate: Fatigue that interferes with normal activity
	3	Severe: Fatigue that prevents normal activity
Gastrointestinal symptoms (nausea, vomiting, diarrhea and/or abdominal pain)	0	Normal
	1	Mild: Gastrointestinal symptoms that are easily tolerated
	2	Moderate: Gastrointestinal symptoms that interfere with normal activity
	3	Severe: Gastrointestinal symptoms that prevent normal activity
Arthralgia	0	Normal
	1	Easily tolerated
	2	Interferes with normal activity
	3	That prevents normal activity
Myalgia	0	Normal
	1	Easily tolerated
	2	Interferes with normal activity
	3	That prevents normal activity
Shivering	0	Normal
	1	Easily tolerated
	2	Interferes with normal activity
	3	That prevents normal activity

*Fever is defined as temperature $\geq 38.0^{\circ}\text{C} / 100.4^{\circ}\text{F}$. The preferred location for measuring temperature in this study will be the oral cavity.

The maximum intensity of local injection site redness/swelling/fever will be scored at GSK Biologicals as follows:

Redness/swelling	
0:	$\leq 20 \text{ mm}$
1:	$> 20 - \leq 50 \text{ mm}$
2:	$> 50 - \leq 100 \text{ mm}$
3:	$> 100 \text{ mm}$

Temperature $> 39^{\circ}\text{C}/102.2^{\circ}\text{F}$ will be considered as grade 3 fever.

The investigator will assess the maximum intensity that occurred over the duration of the event for all unsolicited AEs (including SAEs) recorded during the study. The assessment will be based on the investigator's clinical judgement.

The intensity should be assigned to one of the following categories:

1 (mild)	= An AE which is easily tolerated by the subject, causing minimal discomfort and not interfering with everyday activities.
2 (moderate)	= An AE which is sufficiently discomforting to interfere with normal everyday activities.
3 (severe)	= An AE which prevents normal, everyday activities. In adults, such an AE would, for example, prevent attendance at work/school and would necessitate the administration of corrective therapy.

An AE that is assessed as Grade 3 (severe) should not be confused with a SAE. Grade 3 is a category used for rating the intensity of an event; and both AEs and SAEs can be assessed as Grade 3. An event is defined as ‘serious’ when it meets one of the pre-defined outcomes as described in Section 8.1.2.

Note that the grading of laboratory parameters will be based on the FDA Guidance for Industry “Toxicity Grading Scale for Healthy Adult and Adolescent Volunteers Enrolled in Preventive Vaccine Clinical Trials” (refer to Section 8.1.5 and [APPENDIX C](#)).

8.3.3.2.2. Assessment of causality

The investigator is obligated to assess the relationship between study vaccines/products and the occurrence of each AE/SAE using clinical judgement. In case of concomitant administration of multiple vaccines/products, if possible, the investigator should specify if the AE could be causally related to a specific vaccine/product administered (i.e. investigational, control/placebo or co-administered vaccine). When causal relationship to a specific vaccine(s)/product(s) cannot be determined the investigator should indicate the AE to be related to all products.

Alternative plausible causes, such as natural history of the underlying diseases, concomitant therapy, other risk factors, and the temporal relationship of the event to the study vaccines/products will be considered and investigated. The investigator will also consult the IB and/or SmPC and/or Prescribing Information for marketed products to determine his/her assessment.

There may be situations when a SAE has occurred and the investigator has minimal information to include in the initial report to GSK Biologicals. However, it is very important that the investigator always makes an assessment of causality for every event prior to submission of the Expedited Adverse Events Report to GSK Biologicals. The investigator may change his/her opinion of causality in light of follow-up information and update the SAE information accordingly. The causality assessment is one of the criteria used when determining regulatory reporting requirements.

All solicited local (injection site) reactions will be considered causally related to vaccination. Causality of all other AEs should be assessed by the investigator using the following question: *Is there a reasonable possibility that the AE may have been caused by the study vaccine/product?*

YES : There is a reasonable possibility that the study vaccines/products contributed to the AE.

NO : There is no reasonable possibility that the AE is causally related to the administration of the study vaccines/products. There are other, more likely causes and administration of the study vaccines/products is not suspected to have contributed to the AE.

If an event meets the criteria to be determined as 'serious' (see Section 8.1.2), additional examinations/tests will be performed by the investigator in order to determine ALL possible contributing factors for each SAE.

Possible contributing factors include:

- Medical history.
- Other medication.
- Protocol required procedure.
- Other procedure not required by the protocol.
- Lack of efficacy of the vaccines/products, if applicable.
- Erroneous administration.
- Other cause (specify).

8.3.3.3. Assessment of outcomes

The investigator will assess the outcome of all unsolicited AEs (including SAEs) recorded during the study as:

- Recovered/resolved.
- Recovering/resolving.
- Not recovered/not resolved.
- Recovered with sequelae/resolved with sequelae.
- Fatal (SAEs only).

8.3.3.4. Medically attended events

For each solicited and unsolicited symptom the subject experiences, the subject will be asked if he/she received medical attention defined as hospitalization, or an otherwise unscheduled visit to or from medical personnel for any reason, including emergency room visits. This information will be recorded in the eCRF.

8.4. Reporting of serious adverse events, pregnancies, and other events

8.4.1. Prompt reporting of serious adverse events, pregnancies, and other events to GSK Biologicals

SAEs that occur in the time period defined in Section 8.3 will be reported promptly to GSK within the timeframes described in [Table 23](#), once the investigator determines that the event meets the protocol definition of a SAE.

Pregnancies that occur in the time period defined in Section 8.3 will be reported promptly to GSK within the timeframes described in [Table 23](#), once the investigator becomes aware of the pregnancy.

pIMDs that occur in the time period defined in Section 8.3 will be reported promptly to GSK within the timeframes described in [Table 23](#), once the investigator determines that the event meets the protocol definition of a pIMD.

Table 23 Timeframes for submitting serious adverse event, pregnancy and other events reports to GSK Biologicals

Type of Event	Initial reports		Follow-up of relevant information on a previous report	
	Timeframe	Documents	Timeframe	Documents
SAEs	24 hours*‡	electronic Expedited Adverse Events Report	24 hours*	electronic Expedited Adverse Events Report
Pregnancies	2 weeks*	electronic pregnancy report	2 weeks*	electronic pregnancy report
pIMDs	24 hours***‡	electronic Expedited Adverse Events Report	24 hours*	electronic Expedited Adverse Events Report

*Timeframe allowed after receipt or awareness of the information.

**Timeframe allowed once the investigator determines that the event meets the protocol definition of a pIMD.

‡ The investigator will be required to confirm review of the SAE/pIMD causality by ticking the 'reviewed' box in the electronic Expedited Adverse Events Report within 72 hours of submission of the SAE/pIMD.

8.4.3. Completion and transmission of SAE reports to GSK Biologicals

Once an investigator becomes aware that a SAE has occurred in a study subject, the investigator (or designate) must complete the information in the electronic Expedited Adverse Events Report **WITHIN 24 HOURS**. The report will always be completed as thoroughly as possible with all available details of the event. Even if the investigator does not have all information regarding a SAE, the report should still be completed within 24 hours. Once additional relevant information is received, the report should be updated **WITHIN 24 HOURS**.

The investigator will always provide an assessment of causality at the time of the initial report. The investigator will be required to confirm the review of the SAE causality by ticking the 'reviewed' box in the electronic Expedited Adverse Events Report within 72 hours of submission of the SAE.

8.4.3.1. Back-up system in case the electronic reporting system does not work

If the electronic reporting system does not work, the investigator (or designate) must complete, then date and sign a paper Expedited Adverse Events Report and fax it to the Study Contact for Reporting SAEs (refer to the [Sponsor Information](#)) or to GSK Biologicals Clinical Safety and Pharmacovigilance department within 24 hours.

This back-up system should only be used if the electronic reporting system is not working and NOT if the system is slow. As soon as the electronic reporting system is working again, the investigator (or designate) must complete the electronic Expedited Adverse Events Report within 24 hours. The final valid information for regulatory reporting will be the information reported through the electronic SAE reporting system.

8.4.4. Completion and transmission of pregnancy reports to GSK Biologicals

Once the investigator becomes aware that a subject is pregnant, the investigator (or designate) must complete the required information onto the electronic pregnancy report **WITHIN 2 WEEKS**.

Note: Conventionally, the estimated gestational age (EGA) of a pregnancy is dated from the first day of the last menstrual period (LMP) of the cycle in which a woman conceives. If the LMP is uncertain or unknown, dating of EGA and the estimated date of delivery (EDD) should be estimated by ultrasound examination and recorded in the pregnancy report.

8.4.5. Reporting of pIMDs to GSK Biologicals

Once a pIMD is diagnosed (serious or non-serious) in a study subject, the investigator (or designate) must complete the information in the electronic Expedited Adverse Events Report **WITHIN 24 HOURS** after he/she becomes aware of the diagnosis. The report allows to specify that the event is a pIMD and whether it is serious or non-serious. The report will always be completed as thoroughly as possible with all available details of the event, in accordance with the pIMD standard questionnaire provided. Even if the investigator does not have all information regarding a pIMD, the report should still be completed within 24 hours. Once additional relevant information is received, the report should be updated **WITHIN 24 HOURS**.

The investigator will always provide an assessment of causality at the time of the initial report. The investigator will be required to confirm the review of the pIMD causality by ticking the 'reviewed' box in the electronic Expedited Adverse Events Report within 72 hours of submission of the pIMD.

Refer to Section [8.4.3.1](#) for back-up system in case the electronic reporting system does not work.

8.4.6. Updating of SAE, pregnancy, and pIMD information after removal of write access to the subject's eCRF

When additional SAE, pregnancy or pIMD information is received after removal of the write access to the subject's eCRF, new or updated information should be recorded on the appropriate paper report, with all changes signed and dated by the investigator. The updated report should be faxed to the Study Contact for Reporting SAEs (refer to the [Sponsor Information](#)) or to GSK Biologicals Clinical Safety and Pharmacovigilance department within the designated reporting time frames specified in [Table 23](#).

8.4.7. Regulatory reporting requirements for serious adverse events

The investigator will promptly report all SAEs to GSK in accordance with the procedures detailed in Section [8.4.1](#). GSK Biologicals has a legal responsibility to promptly notify, as appropriate, both the local regulatory authority and other regulatory agencies about the safety of a product under clinical investigation. Prompt notification of SAEs by the investigator to the Study Contact for Reporting SAEs is essential so that legal obligations and ethical responsibilities towards the safety of other subjects are met.

Investigator safety reports are prepared according to the current GSK policy and are forwarded to investigators as necessary. An investigator safety report is prepared for a SAE(s) that is both attributable to the study vaccines/products and unexpected. The purpose of the report is to fulfill specific regulatory and GCP requirements, regarding the product under investigation.

8.5. Follow-up of adverse events, serious adverse events, and pregnancies

8.5.1. Follow-up of adverse events and serious adverse events

8.5.1.1. Follow-up during the study

After the initial AE/SAE report, the investigator is required to proactively follow each subject and provide additional relevant information on the subject's condition to GSK Biologicals (within 24 hours for SAEs; refer to [Table 23](#)).

All MAEs, AEs and pIMDs (serious or non-serious) documented at a previous visit/contact and designated as not recovered/not resolved or recovering/resolving will be reviewed at subsequent visits/contacts until the last visit of the subject.

All AEs documented at a previous visit/contact and designated as not recovered/not resolved or recovering/resolving will be reviewed at subsequent visits/contacts until 30 days after the last vaccination.

8.5.1.2. Follow-up after the subject is discharged from the study

The investigator will follow subjects:

- With MAEs, SAEs, pIMDs (serious or non-serious), or subjects withdrawn from the study as a result of an AE, until the event has resolved, subsided, stabilized, disappeared, or until the event is otherwise explained, or the subject is lost to follow-up.
- With other non-serious AEs, until the event is otherwise explained or they are lost to follow-up.

If the investigator receives additional relevant information on a previously reported SAE, he/she will provide this information to GSK Biologicals using a paper/electronic Expedited Adverse Events Report and/or pregnancy report as applicable.

GSK Biologicals may request that the investigator performs or arranges the conduct of additional clinical examinations/tests and/or evaluations to elucidate as fully as possible the nature and/or causality of the AE or SAE. The investigator is obliged to assist. If a subject dies during participation in the study or during a recognized follow-up period, GSK Biologicals will be provided with any available post-mortem findings, including histopathology.

8.5.2. Follow-up of pregnancies

Pregnant subjects will be followed to determine the outcome of the pregnancy. At the end of the pregnancy, whether full-term or premature, information on the status of the mother and child will be forwarded to GSK Biologicals using the electronic pregnancy report and the Expedited Adverse Events Report if applicable. Generally, the follow-up period doesn't need to be longer than six to eight weeks after the estimated date of delivery.

Regardless of the reporting period for SAEs for this study, if the pregnancy outcome is a SAE, it should always be reported as SAE.

8.6. Treatment of adverse events

Treatment of any AE is at the sole discretion of the investigator and according to current good medical practice. Any medication administered for the treatment of a SAE/pIMD should be recorded in Expedited Adverse Event Report of the subject's eCRF (refer to Section 6.7).

8.7. Subject card

Study subjects must be provided with the address and telephone number of the main contact for information about the clinical study.

The investigator (or designate) must therefore provide a "subject card" to each subject. In an emergency situation this card serves to inform the responsible attending physician that the subject is in a clinical study and that relevant information may be obtained by contacting the investigator.

Subjects must be instructed to keep subject cards in their possession at all times during the study duration.

8.8. Holding rules and safety monitoring

Study holding rules (see Section 8.8.1) and safety monitoring (see Section 8.8.2) have been defined.

The investigator is not permitted to administer Dose 2 of the study vaccine to the subjects enrolled in the Phase I until receipt of the favorable outcome of the IDMC safety evaluation based on safety data collected up to 7 days post-Dose 1 in at least 60 Phase I subjects.

Vaccination in Phase II subjects can only start after receipt of the favorable outcome of the IDMC safety evaluation based on safety data collected up to 7 days post-Dose 1 in all Phase I subjects (N = ~80) (refer to [Enrolment](#) design).

During the entire study period, there will be regular IDMC reviews (monthly during the vaccination phases and every 6 months during the safety follow-up phases).

Dose 3 (booster) can only be administered to Phase II subjects upon favorable outcome of the 7-day post-Dose 3 safety data review of Phase I subjects by the IDMC.

In addition, if any safety concern is identified by the investigator (i.e. meeting of holding rules 1a-1d [see [Table 24](#)] or any other safety concern), he/she should inform GSK Biologicals immediately, and vaccination may be put on hold as a consequence.

If any safety concern is identified in other study(ies) in which the investigational SUIV is used, GSK Biologicals might also request to put the vaccination in this study on hold during the period needed to perform the assessment of safety data of the other study(ies).

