Phase I subjects will be vaccinated one at the time, at least 60 minutes apart, with a maximum of 10 subjects a day. This is applicable for Dose 1 (Day 1), Dose 2 (Day 57) and booster dose (Month 14). Dose 2 can only be provided to Phase I subjects upon favorable outcome of the 7-day post-Dose 1 safety data review by the IDMC of at least 60 Phase I subjects.

- **Treatment allocation:** randomized (1:1:1:1:1:1:1:1 ratio) using GSK Biologicals' Randomization System on Internet (SBIR).
- **Blinding:**

Table 3 **Blinding of study epochs**

Study Epochs	Blinding
Epoch 001	Not applicable
Epoch 002	Observer-blind
Epoch 003	Observer-blind

- **Sampling schedule: (Amended: 11 July 2019)**
 - Blood samples for safety assessment will be drawn from all subjects at all visits: Screening*, Days 1, 8, 29, 57, 64, 85, Month 8, Month 14, Month 14 + 7 days, Month 14 + 28 days, Month 20 and Month 26.

*Only for subjects enrolled in Phase I (refer to the [Enrolment](#) section).
 - Blood samples for serology testing will be drawn from all subjects at Days 1 (Visit 1), 29 (Visit 3), 85 (Visit 6), Month 8 (Visit 7), Month 14 (Visit 8), Month 14 + 28 days (Visit 10), Month 20 (Visit 11) and Month 26 (Visit 12).
 - Blood samples for passive transfer experiment in animals will be drawn from all subjects at Days 1 (Visit 1), 85 (Visit 6), Month 14 (Visit 8)*.
 - Blood samples for cell-mediated immunity (CMI) assessment will be drawn from a sub-cohort of ~225 subjects at Days 1 (Visit 1), 8 (Visit 2), 29 (Visit 3), 64 (Visit 5), 85 (Visit 6), Month 14 (Visit 8)*, Month 14 + 7 days (Visit 9)* **and** Month 14 + 28 days (Visit 10)*. The sub-cohort will consist of the first Phase II subjects enrolled in pre-specified centers.
 - During the entire study period, nasal and throat swabs will be collected as soon as possible (preferably within 24 hours, but not later than 7 days) after the onset of an influenza-like illness (ILI) to test for influenza and/or other respiratory pathogens by RT-PCR **if deemed necessary, or stored for future research** (see Section [5.4.2](#)).

***Note that samples already collected for these timepoints by the time of Protocol Amendment 4 implementation at site will not be tested and will be stored, unless deemed necessary based on medical review of the cases.**

- **ILI surveillance:** ILI is defined as at least one of these systemic symptoms:
 - Temperature (oral) $\geq 37.8^{\circ}\text{C}/98.6^{\circ}\text{F}$ and/or,

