8.8.1. Holding rules

Study holding rules which will be applied during the safety evaluation are defined below.

If a holding rule 1a through 1d is observed by the investigator, it will be reported promptly to GSK within 24 hours. Meeting the other holding rules will be determined by IDMC review of safety data at regular intervals.

These holding rules have been written under the assumption that safety data of all subjects will be available. Therefore, the investigator will be requested to record safety data meeting the criteria of holding rules in the eCRF within 24 hours after reception of the data to ensure that all necessary information are available for IDMC reviews. If the data from all subjects are not available, the holding rules will be assessed on a pro-rata basis.

Upon meeting of any holding rules, further vaccination will be immediately put on hold pending safety review and consultation with the GSK Biologicals' Vaccine Safety Monitoring Board (VSMB), as appropriate.

GSK Biologicals' decision on whether to suspend, modify, or continue the conduct of the study on all groups or on selected groups will be communicated to the investigators, to CBER, and to the IRBs/IECs.

In case of a safety concern, the final responsibility to recommend whether or not the trial should be stopped permanently rests with the sponsor, after having considered all the safety information available. If the trial is stopped, a letter indicating the reasons for stopping the study will be sent to the IRBs/IECs via the investigator(s), and to CBER via GSK Biologicals.

Table 24 Study holding rules

Holding rules	Event	Number/percentage of subjects
1a	Death or any life-threatening SAE.	≥ 1
1b	Any SAE that cannot reasonably be attributed to a cause other than vaccination	≥ 1
1c	Any withdrawal from the study or withdrawal from study vaccine(s)/product(s) (by investigator or subject request) following a grade 3 AE that cannot reasonably be attributed to a cause other than vaccination.	≥ 1
1d	Any local or general solicited AE leading to hospitalization, or fever > 40°C (104°F) (oral route) that cannot reasonably be attributed to a cause other than vaccination, or necrosis at the injection site, within the 7-day (Days 1-7) post-vaccination period.	≥ 1
2a	Any grade 3 solicited local AE lasting 48h or more in an investigational group, within the 7-day (Days 1-7) post-vaccination period.	≥ 30% (and ≥ 2 subjects in one group)

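### Phase II Dose 1 and Dose 3 each wait for IDMC review of the same dose in Phase I, but no planned review of Phase I post-Dose 2 data is tied to Phase II Dose 2 (minor, cheap to improve)

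*Protocol*

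**What the plan says.** Protocol section 8.8 sets conditions on three of the dosing steps.

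- **Phase II Dose 1:** "Vaccination in Phase II subjects can only start after receipt of the favorable outcome of the IDMC safety evaluation" of 7-day post-Dose 1 data in all of the roughly 80 Phase I subjects.
- **Phase I Dose 2:** section 3 states that "Dose 2 can only be provided to Phase I subjects upon favorable outcome of the 7-day post-Dose 1 safety data review by the IDMC", and 8.8 specifies "safety data collected up to 7 days post-Dose 1 in at least 60 Phase I subjects". Section 8.8.2 repeats this.
- **Phase II Dose 3:** "Dose 3 (booster) can only be administered to Phase II subjects upon favorable outcome of the 7-day post-Dose 3 safety data review". The IDMC makes that review on the Phase I data. This condition stands in 8.8 and is not repeated in 8.8.2.

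The only condition on Dose 2 therefore concerns Phase I subjects and uses post-Dose 1 data. No sentence orders Phase II Dose 2 after a review of Phase I post-Dose 2 data.

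Two general provisions apply throughout. On frequency, "there will be regular IDMC reviews (monthly during the vaccination phases and every 6 months during the safety follow-up phases"; section 8.8.2 allows that frequency to be adapted on IDMC advice. On detection, rules 1a to 1d are reported by the investigator within 24 hours, whereas for rules 2a to 2c: "Meeting the other holding rules will be determined by IDMC review of safety data at regular intervals".

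**The concern.** Section 8.8.2 applies Phase I caution to Dose 2 as well as to the other doses: subjects are vaccinated singly, an hour or more apart, with a daily cap of 10. Phase II vaccination has no such limits. The cautious stage thus produces about 24 active second doses (8 in each cH8/5/11 group), yet nothing requires anyone to look at them before Phase II second doses begin.

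Dose 2 is PBS in seven of the ten groups. In the three cH8/5/11 groups it is a second chimeric dose 56 days after the first, and two of those groups are adjuvanted. Post-Dose 1 data cannot show reactogenicity after a second active dose. Rules 2a to 2c are percentages within a group, and the blinded site team cannot readily see that a group has crossed its threshold. If the next monthly review falls after the first Phase II Visit 4, a threshold already crossed in Phase I could go unread while Phase II second doses are given.

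**Working it through.** The protocol gives no figure for this gap, so there is none to reproduce. The check is calendar arithmetic plus exact binomial probabilities.

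**Inputs from the protocol**
- Phase I about 80 subjects, at most 10 per day (8.8.2), so at least 8 days of enrolment.
- Phase II about 390, or 39 per group (section 3). Active at Dose 2: 3 × 39 = 117. Adjuvanted: 2 × 39 = 78.
- Table 7: Visit 1 to Visit 2, 7 days (7–9 allowed); Visit 1 to Visit 4, 56 days (56–66); Visit 4 to Visit 5, 7 days (7–9).
- A month is 28 days (footnote to Table 5).

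**Assumed, because not given**
- r = days from the last Phase I 7-day post-Dose 1 data to Phase II opening; taken as 7, 14, 21 and 28.
- Phase II enrolment of 2, 5 or 10 per day.
- The next monthly review falls 0 to 28 days after the data are ready.
- Data count as sufficient with 60 Phase I subjects, the number that the protocol uses for its own Phase I Dose 2 condition.

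**Step 1: on-schedule visits, fastest Phase I.** Let L be the day of the last Phase I Dose 1. At 10 per day the 60th subject is dosed on L − 2.
- 60-subject post-Dose 2 data ready: L − 2 + 56 + 7 = L + 61.
- Latest next monthly review: L + 61 + 28 = L + 89.
- Phase II opens at L + 7 + r, so the earliest Phase II Dose 2 is L + 63 + r.
- Worst-case gap = 89 − 63 − r = 26 − r, i.e. 19, 12, 5 and 0 days for r = 7, 14, 21 and 28.

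**Step 2: all Phase I visits at their latest limits.** Visit 2 then also moves, to day 9.
- Data ready: L − 2 + 66 + 9 = L + 73. Latest next review: L + 101.
- Phase II opens at L + 9 + r, so the earliest Phase II Dose 2 is L + 65 + r.
- Worst-case gap = 101 − 65 − r = 36 − r, i.e. 29, 22, 15 and 8 days, and 0 from r = 36.

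**Step 3: milder cases.**
- Phase I at 3 per day: the 60th subject is dosed about L − 7, data are ready at L + 56, and the gap is 21 − r (14 and 7 days at r = 7 and 14).
- Monthly reviews counted from the one that opens Phase II, with on-schedule visits and r up to 21: the second falls on day 56, 60 or 62 for months of 28, 30 or 31 days, against an earliest Phase II Visit 4 on day 56. The gap is 0, 4 or 6 days.
- If a review falls as soon as the data are ready, the gap is 0.

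**Step 4: active second doses in the gap.** Three of ten groups are active, so the count is 0.3 × enrolment per day × gap in days. For Step 1:

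| Enrolment per day | r = 7 | r = 14 | r = 21 | r = 28 |
|---|---|---|---|---|
| 2 | 11.4 | 7.2 | 3 | 0 |
| 5 | 28.5 | 18 | 7.5 | 0 |
| 10 | 57 | 36 | 15 | 0 |

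**Step 5: would a review fit before Visit 4?** Suppose it is turned around in r days. On schedule, the outcome arrives at L + 61 + r, 2 days before the first Phase II Visit 4 at L + 63 + r. At the latest limits it arrives at L + 73 + r. The first Phase II subject was dosed at L + 9 + r, so that is day 64, inside the 56–66 day window.

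**Step 6: what such a review could see.** Sixty subjects are about 6 per group, or about 18 active second doses. Rule 2b needs at least 20% and at least 2 subjects, so 2 of 6. At a true 20% rate: 1 − 0.8⁶ − 6 × 0.2 × 0.8⁵ = 1 − 0.262 − 0.393 = 0.345. The same formula gives 0.580 at 30%, 0.767 at 40% and 0.114 at 10%. For at least one of the two adjuvanted groups at 20%: 1 − (1 − 0.345)² = 0.571. With 8 per group the single-group figures at 20%, 30% and 40% are 0.497, 0.745 and 0.894.

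**The case against.** The strongest case against is that nothing in the protocol is wrong or contradictory here, and that much of the period is already covered.

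- **Serious and individual events.** Rules 1a to 1d act on a single subject, and 1c includes withdrawal after a grade 3 event. For any other concern of the investigator, "he/she should inform GSK Biologicals immediately, and vaccination may be put on hold as a consequence". Laboratory results go promptly to investigators (5.7.3), and unexplained, clinically significant grade 3 results prompt a recommended recall and repeat test (8.1.5). This stands. A reader might infer that a serious second-dose event could pass unnoticed into Phase II; the text does not support that.
- **Partial data.** "If the data from all subjects are not available, the holding rules will be assessed on a pro-rata basis" A monthly review can act before all Phase I data are in. This stands and shortens the gap.
- **Dose 3 differs.** cH11/1N1 is first given at Month 14, after a period of six-monthly reviews, while cH5/1N1 in all three formulations had already been reviewed as a first dose. A reader might infer that the missing Dose 2 condition is an inconsistency or an oversight. These differences give the Dose 3 condition its own reasons, so that inference fails. They do not make first-dose data informative about a second active dose.
- **Unseen sources.** Section 8.8.2 leaves operational details to the IDMC charter, and Figure 1 is not shown. Either may set the review date, so the point concerns the protocol text only.
- **Stacked assumptions.** The 19-day case needs the fastest Phase I enrolment, r = 7 and a review only just missed. This stands, which is why ranges are given.
- **Timing.** By Amendment 4 the Day 85 interim analysis had been reviewed and development dropped. The point can only be about the staggering scheme as written.

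**Conclusion.** The point holds in a narrow form and is minor. The protocol does not require Phase I post-Dose 2 data to be reviewed before Phase II Dose 2, and group-level grade 3 findings under rules 2a to 2c could therefore wait for the next monthly review. The exposure lasts days to a few weeks at worst and may be nil. The size rests on r, enrolment speed and review dates, none of which the protocol gives. Confidence is medium, because the charter may already fix the timing.

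A reader might go further and ask for a hard stop on Phase II Dose 2 in all ten groups until a favorable outcome is issued. The documents do not clearly support that. Seven of those groups receive PBS at Dose 2, and a late review would push Visit 4 against a 10-day window whose breach can remove subjects from the per-protocol set, and with them Day 85 data for the primary immunogenicity endpoints.

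**What to change.** In sections 8.8 and 8.8.2, state that one of the planned monthly IDMC reviews will be scheduled so that 7-day post-Dose 2 data from at least 60 Phase I subjects are assessed against the existing holding rules before the first Phase II Visit 4. Vaccination is held only if a rule is met or the IDMC advises it.

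The cost is a sentence in the protocol, matching charter wording, and the date of one review already due. No new committee, data collection or holding rule is needed. There are three limits:

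- Sensitivity is modest, about one chance in three of meeting rule 2b in a single group of 6 at a true 20% rate.
- A group of 6 with a true 10% rate would meet the rule about 11% of the time, a risk that the monthly reviews already carry.
- If the review runs late and Visit 4 is made to wait, there is a small risk to the 56–66 day window for the earliest Phase II subjects.
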